This pilot RCT began data collection in May 2017 and continued through May 2018. A total of 45 youths and their families were recruited. Data was collected at four time points: baseline (recruitment), 1-month, 3-months, and 6-months. At baseline, caregivers completed a general information form on demographics and medical history, as well as measures to assess health status (Asthma Control Test), and health literacy (S-TOFHLA and Asthma Numeracy Questionnaire). Patients completed measures to assess health status (Asthma Control Test), health literacy (S-TOFHLA) and reading comprehension (WIAT-III), and complete pulmonary function testing (spirometry). Qualitative methods were used to gather acceptability and feasibility data. Participants in both groups were provided with their first canister or diskus of medication in order to attach the electronic adherence monitor at baseline. Participants refilled with medications they purchase as needed for the remainder of the study. One month after initial visit, families were called to complete the Asthma Control Test and study-specific satisfaction survey. Three months after initial visit, families returned to clinic for follow up with the physician and to complete the Asthma Control Test, AAP knowledge interview, and pulmonary function testing (patient only). Six months after initial visit, families returned to clinic for follow up with the physician and to complete the Asthma Control Test, AAP knowledge interview, satisfaction survey, spirometry (patient only), and to review adherence data and return the inhaler monitor. Six families completed follow up measures at 3 months due to time constraints.

The findings of this study will be relevant to research and practice with rural youths with asthma, as well as families with significant literacy issues. A novel and innovative stakeholder-led approach was used in this study to develop a more accessible and effective approach to asthma education in pediatric settings. The process and findings of this study will be widely disseminated and guide improvements to the PAAP for use in future research and practice, including the possible development of an "app" version of the PAAP.

Study Analysis Plan

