All analysis was conducted using SAS 9.4. Descriptive analysis was conducted on baseline measures for both the total sample, and by treatment group. Frequency and valid percentages were used to describe categorical data, means and standard deviations for continuous data, and medians and interquartile range for non-normal continuous data. Group differences were tested by chi-square, Fisher's exact, Mann-Whitney, or t-test as appropriate for variable type, with odds ratios (OR) and 95% CI of the OR, means by group and t-statistic, or mean score ranks and Z-statistic reported.

Generalized linear mixed model (GLIMMIX) with multinomial response distribution and a cumulative logit link function were used to analyze the daily adherence data, in order to model the ordinal outcome measure (0%, 25%, 50%, 75%, and 100% adherence) over time. Multiple covariance structure models were tested, with an unstructured matrix best fitting by AIC. Because adherence changed depending on prescription, the models were tested by both interaction of prescription and by stratification. Sensitivity analysis was also run for 3 months or less data and compared to the full 6 month dataset. Fixed effects were reported. Generalized linear mixed model (GLIMMIX) with binary response distribution was also conducted for the binary outcome of ACT cut-off ≥ 19 .

Linear mixed models with restricted estimation maximum likelihood estimation and Kenward-Richardson adjustment for the degrees of freedom were used for the continuous outcome data. Pre-post analysis included combining 3 month and 6 month time points for outcome measures where the final time point was 3 instead of 6 months. Time was treated as categorical for these pre- post- time points; otherwise time was treated as continuous variable. Time, Group, and Time by Group interaction effects were included in the model. Random effects statement included the time, with participants listed by ID. Different covariance structures and intercept inclusion were tests; AIC was used to determine best model fit with the best fitting model including no intercept and an unstructured covariance matrix. Fixed effects are reported. Sensitivity analysis was also run by including days in the study for those post-outcomes where some participants have 3 months or less data and compared to the full 6 month dataset.

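### For any outcome modelled with continuous time, the no-intercept random-time structure is a lone random slope; it misstates the Time by Group standard error in a direction the plan leaves open

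*Combined protocol and SAP*

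**What the plan says.** The linear mixed model paragraph of the Study Analysis Plan covers the continuous outcomes. Its fixed effects are time, group and their interaction. On the random part it says: "Random effects statement included the time, with participants listed by ID". On model choice it says: "Different covariance structures and intercept inclusion were tests", and then: "AIC was used to determine best model fit with the best fitting model including no intercept and an unstructured covariance matrix".

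Time is categorical in the pre-post analyses, which involved "combining 3 month and 6 month time points for outcome measures where the final time point was 3 instead of 6 months". For everything else, "otherwise time was treated as continuous variable". The paragraph does not name the continuous-time outcomes, the numeric coding of time, the candidate models or any separate residual structure.

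The Methods section gives four data-collection points: baseline, 1, 3 and 6 months. The ACT is listed at all of them, including "One month after initial visit, families were called to complete the Asthma Control Test" and "Six months after initial visit, families returned to clinic for follow up with the physician and to complete the Asthma Control Test". The same section notes: "Six families completed follow up measures at 3 months due to time constraints".

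The last paragraph of the Study Analysis Plan takes the equivalence test from the output of the best-fitting mixed model.

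**The concern.** One sentence on random effects has to serve two kinds of model. With time as a class variable, random time without an intercept gives each occasion its own effect with free variances and covariances, so the marginal covariance is unrestricted. With time as a number, the same statement gives each child one random slope and nothing else. The unstructured matrix then has a single element, and nothing represents stable differences between children at baseline.

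Time by Group is the treatment comparison in a trial of 45 families, and its standard error depends on the covariance model. If that model cannot take the shape of the data, the superiority test has the wrong error rate or loses power. The equivalence test inherits the problem wherever it uses such a model.

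**Working it through.** The plan gives no standard error, variance, correlation or AIC value, so there is no figure of its own to reproduce.

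**Inputs from the documents.** 45 children; visits at 0, 1, 3 and 6 months; 6 families ending at month 3; fixed effects time, group and interaction.

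**Assumed inputs.** Arms of 23 and 22; early finishers split 3 and 3; variance 1 at baseline; the true covariance; the time coding (0/1/3/6, 1/2/4/7, or visit number 1 to 4); a two-sided 5% test.

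**Step 1: the implied covariance.** With slope variance τ² and residual variance σ², the covariance between occasions j and k is τ²·t_j·t_k, and the variance at occasion j is σ² + τ²·t_j².
- Coded 0/1/3/6: baseline with any later visit, τ²·0·t_k = 0. Months 1 and 3, 3τ². Months 3 and 6, 18τ².
- Coded 1 to 4: first two visits, 1·2·τ² = 2τ². Last two, 3·4·τ² = 12τ², six times as large.
- Coded 1/2/4/7: first two, 2τ². Last two, 4·7·τ² = 28τ², fourteen times as large.

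So no coding allows the equal covariances that stable differences between children would produce, and shifting the time origin changes the model.

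**Step 2: effect on the standard error.** Take a true covariance Ω and choose τ² and σ² to bring the working covariance V as close to it as REML would on average. Let A = Σ X′V⁻¹X and B = Σ X′V⁻¹ΩV⁻¹X, summed over children. The reported standard error comes from A⁻¹ and the true one from A⁻¹BA⁻¹, each at the Time by Group element. Ratios of reported to true:
- Exchangeable correlation 0.1 and 0.2: 1.07 and 1.15 (0/1/3/6); 1.06 and 1.14 (1/2/4/7); 1.04 and 1.09 (visits 1 to 4).
- The same plus a true random slope, SD 0.15 per month: 1.05 and 1.10 (0/1/3/6); 0.98 and 1.03 (1/2/4/7); 0.93 and 0.96 (visits 1 to 4).
- Slope SD 0.25 per month: 0.92 to 0.95 (1/2/4/7); 0.83 to 0.85 (visits 1 to 4).
- Serial correlation decaying at 0.3 to 0.6 per month: 0.96 to 0.98 (0/1/3/6); 0.94 to 0.96 (visits 1 to 4). At 0.7 and 0.8 per month, coded 0/1/3/6, the ratio is 1.04 and 1.16.

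**Step 3: effect on the test.** For ratio k, the normal-approximation type I error is 2[1 − Φ(1.96k)].
- k = 1.15: 1.96 × 1.15 = 2.25, giving 2.4%.
- k = 0.98: 1.96 × 0.98 = 1.92, giving 5.5%.
- k = 0.83: 1.96 × 0.83 = 1.63, giving 10.4%.

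For an effect with 80% power under the correct model, power is about Φ(2.80 − 1.96k): 76% at k = 1.07 and 71% at k = 1.15.

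**Step 4: where AIC could have chosen this model.** Trials were simulated with time coded 0/1/3/6. How often AIC kept the lone slope depends on the candidates, which the plan does not list. Figures are for correlations of 0.1, 0.2 and 0.3.
- No true slope, intercept-plus-slope the only rival: 68%, 25% and 5%.
- No true slope, random intercept alone also a candidate: 20%, 6% and 1%.
- All three candidates and a true slope of SD 0.15: 69%, 34% and 10%.

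With all three candidates, then, AIC keeps the lone slope most often when slopes truly vary. That is the case in which Step 2 shows the sign of the error turning on the coding.

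**The case against.** **The sentence may describe only the pre-post models.** An unstructured matrix has content for categorical time and none for one continuous slope, and the equivalence paragraph speaks of group and time-point means. The six families who finished at month 3 could put the ACT in the pre-post set. This stands as a reason for caution: that any particular outcome was fitted with a lone slope is an inference. It does not clear the text, which provides for continuous time in the same paragraph. If the sentence is for pre-post models only, the continuous-time models have no stated covariance.

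**The unstructured matrix may be the residual matrix.** Then the covariance is adequate, and a random slope on top of it is redundant. The wording does not exclude this, but the statement follows directly on the random effects and the intercept test, and no residual structure is mentioned.

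**An intercept was tested and AIC rejected it.** This narrows the plausible truths to weak stable differences or sizeable slope variation. It does not make the chosen covariance adequate: in a sample this small, AIC can drop an intercept that matters for the standard error.

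**A reader might infer that the test is simply conservative, so no false efficacy claim could follow.** That holds under exchangeable correlation, but ratios below 1 arise under equally ordinary assumptions and a coding the plan does not exclude. A reader might also take up the much larger ratios at exchangeable correlations of 0.3, 0.5 and 0.7 (1.25, 1.52 and 2.01, coded 0/1/3/6). AIC run on the outcome itself would rarely or never keep the lone slope there. Those ratios would need the structure to have been carried over from another outcome, which the documents do not state.

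**This is a pilot with no stated power target.** True, and it limits the weight of the point. The plan nonetheless states superiority hypotheses and an equivalence conclusion, and both depend on these models.

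**Conclusion.** The point holds in conditional form, without a fixed sign. As written, any continuous-time outcome gets a lone random slope, which restricts within-child covariance in a way the design does not justify; the categorical pre-post models are unaffected. The ACT is the probable case because it alone is listed at all four time points, but the documents do not confirm it.

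The error in the Time by Group standard error runs from about 15% too large to about 17% too small (1 − 0.83) over the weak exchangeable, true-slope and 0.3 to 0.6 serial-decay cases examined. All of these rest on assumed covariances and codings. The effect on equivalence cannot be sized, because the plan gives no formula for the test. Confidence is medium: the algebra is certain, its application to a named outcome is not. The specification should be changed, but nothing here shows that a reported result is wrong.

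The point does not extend to the separate generalized models for daily adherence and for the binary ACT cut-off.

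**What to change.** Limit the no-intercept unstructured specification to the categorical pre-post models, and say so. Name each continuous-time outcome and state how time was coded.

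For each such outcome use one of the following, whatever AIC says about the intercept:
- a random intercept plus time: `RANDOM INTERCEPT time / SUBJECT=ID TYPE=UN`; or
- in place of the RANDOM statement, a by-visit residual matrix: `REPEATED visit / SUBJECT=ID TYPE=UN`, keeping time continuous in the fixed effects.

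Rerun the equivalence test from any model that changes.

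The cost is one line of SAS per model, a refit and a few sentences of plan text, with no new data. The lone slope has 2 covariance parameters. The random-intercept version has 4 (two more), and the four-visit matrix has 4 × 5 / 2 = 10 (eight more). With 45 children the larger matrix is the more demanding to estimate, so the first option is the lighter one.

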of pictorial & written AAPs. Our working hypothesis is that relative to usual care (Written AAP), Pictorial AAP will produce superior clinical and behavioral outcomes: (a) better treatment plan knowledge for caregiver and patient; (b) higher daily adherence rates to preventive medication (via electronic monitoring); and (c) better health outcomes (i.e., report of better asthma control & higher *lung functioning* or spirometry scores). This hypothesis is based in part on research findings indicating that use of pictures in health education markedly increases recall of information through simpler and more salient cues.

Specific Aim # 2 – Evaluate provider and family acceptability of pictorial AAP. Based on existing literature, we expect that the Pictorial AAP will be easy and user-friendly for providers to offer as well as patients and families to use. Consequently, our working hypothesis is that patient and caregiver satisfaction (e.g., perceived ease of use, benefits) survey scores will be significantly higher for the Pictorial AAP than for the Written AAP group.

Specific Aim # 3: Identify whether parent health literacy and youth literacy levels are associated with treatment outcome. Pearson (parametric) or Spearman (non-parametric) correlations will be used as appropriate to assess the association between parent health literacy and youth literacy to changes in knowledge, adherence, and health outcome, as well as caregiver and patient satisfaction, within and between AAP groups. Given that research suggests the use of graphics and images improves comprehension of medical information, it is anticipated that rural youth, particularly with lower literacy levels, will benefit significantly from a simpler, “image rich” pictorial AAP.

Design: Pilot Randomized Controlled Trial

Young people aged 8-17 were randomly assigned to one of two groups (pictorial vs. written AAP, i.e. usual care) for 6 months. The Written AAP (WAAP) group received a personalized, text-based AAP. The WAAP is consistent with national practice guidelines [5] and recommended as standard care for patients with asthma. The proposed study will use the written AAP published by the National Heart Lung and Blood Institute (NHLBI) (Available at: https://www.nhlbi.nih.gov/files/docs/public/lung/asthma_actplan.pdf). Providers (not researcher) completed the WAAP with the child's prescribed medications and specific asthma care regimen. The provider reviewed the WAAP with the child and caregiver.

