Finally, equivalence testing was conducted for all continuous outcomes, assuming that results that fall within an SD unit difference would indicate that PAAP is as good as guideline-recommended care (WAAP) with sufficient power. The overall stability of the effect of the treatment response was demonstrated utilizing the F test for equivalence of the effect of psi-squared, a standardized measure of difference between groups/time point means and an overall (across groups and time points) mean. This was be assessed utilizing output from the best-fitting general linear mixed model and by testing whether this psi-squared effect size measure falls in the critical region [6].

References

1. Akinbami, L. J., & Schoendorf, K. C. (2002). Trends in childhood asthma: Prevalence, health care utilization, and mortality. *Pediatrics*, 110(2), 315-322.
2. Akinbami, L. J., Moorman, J. E., & Liu, X. (2011). Asthma prevalence, health care use, and mortality: United States, 2005-2009 (Report No. 32). Atlanta, GA: National Health Statistics Reports, Centers for Disease Control and Prevention; <http://www.cdc.gov/nchs/data/nhsr/nhsr032.pdf>. Updated January 12, 2011. Accessed May 4, 2014.
4. Forbis, S. G., & Ailigne, C. A. (2002). Poor readability of written asthma management plans found in national guidelines. *Pediatrics*, 109, e52.
5. National Heart, Lung, and Blood Institute (2007). National Asthma Education and Prevention Program (NAEPP) Expert Panel Report 3, *Guidelines for the Diagnosis and Management of Asthma* (NIH Publication No. 08-4051).
6. Wang, F., & Amrhein, J. (2016, April 18-21). *Equivalence Tests*. Paper presented at the Proceedings of the SAS®Global Forum 2016., Las Vegas, NV

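### A 1 SD equivalence margin can at most exclude differences of 1 SD or more; passing it does not show that PAAP is as good as WAAP

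*Combined protocol and SAP*

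**What the plan says.** The last paragraph of the Study Analysis Plan states that "equivalence testing was conducted for all continuous outcomes". The rule for reading the results follows: "assuming that results that fall within an SD unit difference would indicate that PAAP is as good as guideline-recommended care (WAAP) with sufficient power". It does not say whether the SD is of the raw score, the change or the model residual, nor from which arm or time point. It gives no margin in scale units, no clinical rationale, no alpha and no power figure.

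The same paragraph then says: "The overall stability of the effect of the treatment response was demonstrated utilizing the F test for equivalence of the effect of psi-squared". It describes psi-squared as "a standardized measure of difference between groups/time point means and an overall (across groups and time points) mean", and refers to reference 6, a conference paper on equivalence tests, for the critical region. No numerical bound is given.

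For the continuous outcomes, the linear mixed model paragraph of the same section says "Time, Group, and Time by Group interaction effects were included in the model" and that fixed effects are reported. It does not promise a confidence interval for the PAAP-versus-WAAP contrast. Specific Aim # 1 is a superiority hypothesis: "relative to usual care (Written AAP), Pictorial AAP will produce superior clinical and behavioral outcomes". No aim states equivalence.

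**The concern.** An equivalence test licenses one statement: the difference is smaller than the margin. With a margin of 1 SD, a pass leaves every smaller deficit open. The plan nevertheless turns a pass into parity with guideline-recommended care, for knowledge, asthma control and spirometry alike, under one common rule.

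If superiority is not shown on an outcome, the parity statement is the one likely to be carried forward, although no clinical argument supports the width of the margin. The Methods say that the findings will be disseminated widely and will inform later research and practice, so the wording of the conclusion matters.

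The named test adds a second doubt. It is introduced for the stability of the treatment response, and it is unclear whether it is also the test of the SD margin.

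**Working it through.** There is no stated power, alpha or sample-size calculation to reproduce. What follows illustrates what a 1 SD margin allows; it does not give the operating characteristics of the psi-squared test.

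**Inputs from the document.** 45 youths recruited, and six families with final measures at 3 months (Methods); two randomised groups (Design); a margin of an SD unit (Study Analysis Plan), read here as 1 SD.

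**Assumed inputs.** About 1:1 split; two one-sided t-tests (TOST) at one-sided 5%, with 2.5% as an alternative; one post-treatment contrast; the SD is that of the raw score, set to 1. The number analysed is not stated, so 45, 39, 36 and 30 are shown.

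**Step 1: what passes with 45 analysed (22/23).**
- SE = sqrt(1/22 + 1/23) = 0.298 SD, with 43 df and t(0.95) = 1.681.
- 90% CI half-width = 1.681 × 0.298 = 0.501 SD.
- A pass needs an observed difference below 1 − 0.501 = 0.499 SD in size.
- Example: an observed PAAP deficit of 0.45 SD passes. Its 90% CI runs from 0.951 SD worse to 0.051 SD better. Its 95% CI (half-width 0.601) runs from 1.051 SD worse to 0.151 SD better.

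**Step 2: how often equivalence is declared (22/23, one-sided 5%).** At true PAAP deficits of 0, 0.3, 0.5, 0.8 and 1 SD the rates are 90%, 74%, 50%, 16% and 5%. The figure at 0.5 SD can be checked by hand: Φ((0.499 − 0.500)/0.298) ≈ 0.50.

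**Step 3: sensitivity at a true deficit of 0.5 SD.** The largest passing difference is L = 1 − t × SE, and the pass rate is approximately Φ((L − 0.5)/SE).

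| Analysed | One-sided alpha | SE | L | Pass rate |
|---|---|---|---|---|
| 45 | 5% | 0.298 | 0.499 | 50% |
| 39 | 5% | 0.320 | 0.460 | 45% |
| 36 | 5% | 0.333 | 0.436 | 43% |
| 30 | 5% | 0.365 | 0.379 | 37% |
| 45 | 2.5% | 0.298 | 0.399 | 37% |

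**Step 4: difference in change.** This corresponds to a two-point Time by Group contrast. The SE is multiplied by sqrt(2(1 − ρ)), where ρ is an assumed pre-post correlation. With 45 analysed, one-sided 5% and a margin of 1 raw SD:
- ρ = 0.3: SE 0.353, pass rate 40%.
- ρ = 0.5: SE 0.298, pass rate 50%.
- ρ = 0.7: SE 0.231, pass rate 69%.

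**Step 5: why the choice of SD matters.** The SD of change divided by the raw SD is sqrt(2(1 − ρ)) = 1.18, 1.00 and 0.77 at ρ = 0.3, 0.5 and 0.7. If the margin is 1 SD of change, the same true deficit of 0.5 raw SD passes 60%, 50% and 32% of the time, against 40%, 50% and 69% in Step 4. The two readings move in opposite directions as ρ rises, so the plan's rule cannot be evaluated until the SD is named.

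**Step 6: psi-squared.** Suppose, as an assumption, that it is the sum of squared standardised deviations of the means from the overall mean. For two equal groups each mean lies d/2 from the overall mean, so psi-squared = 2 × (d/2)² = d²/2. A bound of 0.5 would then correspond to d = 1 SD, and a bound of 1 to d = sqrt(2) = 1.41 SD. Without the bound and the list of means included, a pass cannot be translated into a limit on the difference between arms.

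**The case against.** The case for leaving the text alone has several parts.

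*This is a pilot.* The overall aim is acceptability and feasibility, and the equivalence analysis comes last and belongs to no aim. That limits its weight, but the text still states a conclusion rule for all continuous outcomes.

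*Estimates will be visible.* Fixed effects are reported and Time by Group is in the model. This stands, and a reader who infers that the plan conceals the size of any deficit goes too far. What is not promised is a confidence interval for the contrast.

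*TOST is not the named test.* Correct. The rates above are not the plan's error rates, and they depend on assumed arm sizes, alpha, correlation and numbers analysed. The logical point about the margin needs none of them.

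*Psi-squared is defined elsewhere.* The critical region is referred to a source that is not available here, and the description is compressed. A reader might infer that the measure certainly ignores direction and certainly mixes in time effects. That follows from one reading of the sentence and is not established.

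*The analysis is not written as a fallback.* Equivalence testing is stated unconditionally. That it would be used to rescue a failed superiority result is an inference about use, not something the plan says.

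**Conclusion.** The concern holds: the conclusion rule is wrong as written. Whatever the data show, passing a 1 SD margin can at most exclude differences of 1 SD or more, and nothing elsewhere in the document supplies a justified margin or an interval for the contrast. This rests only on reading an SD unit as 1 SD.

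The illustrated size is that a true 0.5 SD deficit would be called parity about half the time with 45 analysed. The rate is 37% to 50% across the numbers analysed and the two alphas, and 40% to 69% for difference in change at correlations of 0.3 to 0.7, with a raw-SD margin. The document gives no outcome SDs or minimal important difference, so none of this can be put in scale units.

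A reader might go further and say that 45 participants have almost no power at a tighter margin such as 0.5 SD. The document does not support that as a general statement. It names no such margin, and the answer depends on the estimator. With no true difference, power is about 6% for the post-treatment contrast and 37% for difference in change at correlation 0.7. For a baseline-adjusted contrast it is about 10%, 21% and 49% at correlations 0.3, 0.5 and 0.7.

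**What to change.** - Replace the as-good-as conclusion with the statement that differences of 1 SD or more are excluded. Use it only for outcomes where the direct PAAP-versus-WAAP contrast from the linear mixed model supports it.
- Name the SD that defines the margin.
- Label the equivalence analysis exploratory and secondary to the Specific Aim # 1 superiority hypothesis.
- For each continuous outcome, report PAAP minus WAAP with 90% and 95% CIs in scale units. Use the difference in change where a baseline exists (the Methods list the Asthma Control Test and spirometry at baseline). Otherwise use the post-treatment difference (no baseline is listed there for the AAP knowledge interview or satisfaction survey).
- If psi-squared is kept, state its bound and whether it tests the 1 SD margin, and do not rest any statement about PAAP versus WAAP on it alone.
- Do not add a power claim at a narrower margin, since the document supplies none of its inputs.

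The cost is wording and reporting. The contrast and its intervals come from the model already fitted, and no new data are needed. The downside for the sponsor is a less favourable conclusion, although a narrow interval on a given outcome would allow a stronger statement than pass or fail.

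### The claim that PAAP is as good as WAAP most naturally asks whether PAAP is not worse, but the only test named has no sign, so a PAAP benefit lowers the chance of supporting it

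*Combined protocol and SAP*

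**What the plan says.** The final paragraph of the Study Analysis Plan states that "equivalence testing was conducted for all continuous outcomes". Its criterion for the claim is given in the words "assuming that results that fall within an SD unit difference would indicate that PAAP is as good as guideline-recommended care (WAAP) with sufficient power". That margin carries no direction, and the SD it refers to is not identified.

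The one statistic named comes in the next sentence. Stability of the treatment response was shown "utilizing the F test for equivalence of the effect of psi-squared", which is described as "a standardized measure of difference between groups/time point means and an overall (across groups and time points) mean". No alpha, critical value or psi-squared limit is given; the rule is left to a cited conference paper. Non-inferiority is not mentioned.

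The hypotheses point one way. Under Specific Aim # 1, "Pictorial AAP will produce superior clinical and behavioral outcomes", and Specific Aim # 2 expects higher satisfaction with PAAP. The Design section presents WAAP as usual care and as the recommended standard. The Study Analysis Plan separately fits mixed models with Time, Group and Time by Group effects.

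**The concern.** When a new format is compared with the recommended standard and is expected to beat it, calling it as good as the standard most naturally means that it is not worse. That question has one direction. A squared distance has none: PAAP ahead by half an SD and PAAP behind by half an SD give the same psi-squared and the same verdict on equivalence. No aim asks the trial to rule out that PAAP is better.

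At stake is the fallback conclusion. With 45 families, superiority will often be missed for a moderate benefit, and that is when the fallback claim matters. The nearer the truth is to the working hypothesis, the less likely this test is to support the claim.

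**Working it through.** **Inputs from the documents.** 45 youths recruited in total, and six families with follow-up measures at 3 months (Methods); two randomised groups (Design); a margin of one SD unit and an F test on psi-squared (Study Analysis Plan, last paragraph). There is no stated power or critical value to reproduce.

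**Assumptions.** Arms of 22 and 23 (19 and 20 as a loss scenario), alpha 0.05, one continuous outcome, one time point, no covariates.

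**Step 1: translate the margin.** For two equal arms whose means differ by d SD, each mean lies d/2 from the overall mean, so psi-squared = 2 × (d/2)² = d²/2. One SD gives 0.5. Because d is squared, its sign drops out whatever the alpha, sample size or limit.

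**Step 2: critical value.** Equivalence is declared when F lies below the 5% quantile of a noncentral F on 1 and 43 df with noncentrality 22.5 × 0.5 = 11.25. That quantile is 2.86.

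**Step 3: pass rates.** The signed rule asks that the lower confidence limit of PAAP minus WAAP exceed −1 SD. Superiority asks that the lower 95% limit exceed 0. All columns use 22 v 23.

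| True difference (SD) | Psi-squared F, 5% | Signed rule, one-sided 5% | Signed rule, 95% CI | Superiority |
|---|---|---|---|---|
| −0.8 | 16% | 16% | 10% | about 0 |
| −0.5 | 50% | 50% | 37% | about 0 |
| 0 | 90% | 95% | 91% | 2.5% |
| +0.5 | 50% | 99.9% | 99.8% | 37% |
| +0.8 | 16% | about 100% | about 100% | 75% |

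At a true difference of 1 SD in either direction the F test passes 5%. Two one-sided t tests at ±1 SD agree with the F test to within about 0.2 percentage points. At a common 5% level the comparison at zero is 95% v 90%; the 95% CI column is a one-sided 2.5% rule.

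**Step 4: trials with neither conclusion.** At +0.5 SD, simulation with the t-based equivalence test gives about 14% (22% with 19 v 20), and in nearly all of these the 95% CI excludes PAAP being worse by more than 1 SD. At +0.8 SD it is about 10%. The F version is slightly lower. Superiority needs F above 2.017² = 4.07 and equivalence needs F below 2.86, so the two cannot both occur, and at +0.5 SD the remainder is 1 − 0.374 − 0.501 = 0.125.

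**Step 5: where those trials lie.** With an observed SD of 1, the standard error is √(1/22 + 1/23) = 0.298. Equivalence passes up to 1 − 1.681 × 0.298 = 0.50 SD, and superiority passes from 2.017 × 0.298 = 0.60 SD. On the benefit side the gap is therefore an observed difference of roughly 0.50 to 0.60 SD, where the lower 95% limit runs from about −0.10 to 0.

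**Step 6: sensitivity.** At +0.5 SD the F test passes 17%, 50% or 90% for psi-squared limits of 0.25, 0.5 or 1.0, and 38% for limit 0.5 at alpha 0.025. The levels move; the symmetry stays.

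**Step 7: the documented statistic also pools time points.** In a rough four-cell version (22 per cell, cells treated as independent, limit 0.5), the pass rate is 75% with no change at all and 22% when both arms improve equally by 0.5 SD. Adding a 0.8 SD PAAP benefit at follow-up to that improvement leaves 0.1%; a 0.8 SD deficit leaves 14%. So the exact symmetry belongs to the between-arm contrast. Once both arms improve, a benefit can be penalised more than an equal harm.

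**The case against.** The plan says equivalence openly, and the claim can be read loosely as equivalent. The psi-squared test is introduced for stability of the treatment response, in a separate sentence from the SD criterion. That it alone decides the claim is a fair inference, but it is not stated, and the decision rule sits in a reference that is not available here. The percentages describe a two-arm, single-time contrast, not the pooled statistic. All of this stands as a limit on precision. It does not remove the mismatch: the margin and the only named statistic are both unsigned, and the plan never says how to read a result that is superior but not equivalent.

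Three stronger readings are tempting and unsupported.

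- A reader might infer that trials with neither conclusion clearly exclude PAAP being worse. They do not. Failing superiority means the 95% CI does not lie wholly above zero; what nearly all of them exclude is PAAP being worse by more than 1 SD.
- A reader might infer that the plan hides a real benefit. The mixed models report signed group effects, and at +0.8 SD superiority passes about 75% of the time.
- A reader might infer that the lack of sign produces false claims. Passing both one-sided tests implies passing the non-inferiority test at the same margin and alpha, and the F version passes only 5% of the time at −1 SD. The lack of sign costs power only.

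**Conclusion.** The concern holds as a mismatch between a claim that most naturally has one direction and a test that has none. A PAAP benefit lowers the chance of supporting the claim without making failure certain. In the two-arm illustration the pass rate falls from 90% at no difference to 50% at +0.5 SD and 16% at +0.8 SD, the same as for equal harms. The practical loss is smaller, because superiority catches much of it: about 14% of trials reach neither conclusion at +0.5 SD and about 10% at +0.8 SD.

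The sign symmetry of the between-arm contrast needs no assumption. The percentages rest on near-equal arms, alpha 0.05 and a psi-squared limit of 0.5, none of which the documents state. In a 45-family pilot aimed at acceptability and feasibility, with damage confined to one fallback conclusion, this is a moderate point and a cheap improvement.

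**What to change.** For each continuous outcome, report the model-based PAAP minus WAAP difference at the final time point with its 95% CI, scored so that higher is better. Read the lower limit in order: above minus the margin supports not worse by more than the margin; above zero supports superior. Both readings use one interval, so the ordering adds no alpha penalty within an outcome.

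The Study Analysis Plan describes completed analyses, and data collection ran to May 2018 while the document is dated 5/29/2020. The new reading must therefore be labelled post hoc and reported beside the psi-squared result.

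State also that the 1 SD margin is wide and given no rationale. Changing direction does not justify it: with that margin the signed rule still passes about 37% of the time when PAAP is truly 0.5 SD worse.

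The work is one contrast per outcome from the existing models, plus wording; no new data are needed. The price is the post hoc status, which matters because the signed rule is easier to pass whenever PAAP is no worse, and the loss of any claim that PAAP is not better, which no aim asks for.
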